Adherence to treatment (mediator) will be measured in the following ways: (1) Number of sessions attended; (2) Therapist ratings of homework compliance (0-100%) based on written assignment review and patient report after each session. Composite adherence score will be calculated on a 10-point Likert scale ranging from 0 (Almost never/never adherent) to 10 (Always adherent).

Timeline

The first 3 months of the project are designed to hire staff, train clinicians, the blind raters, and VRAs (Table 3). There will be a total of 7 overlapping study waves, each lasting 12 months, in which we will enroll 9-10 patients. During the last 3 months of the project, we will finalize data analysis, publish the results and determine the next step for competitive funding.

Statistical Plan

Missing data will be minimized by intensive training of the raters in techniques of clarifying answers and checking questionnaires while Veteran participants are on-site. When missing values are identified, several approaches to acquire the necessary data will be employed: (1) if at all possible, Veteran participants will be rescheduled within 24 hours of completion of tests or interviews; (2) if a participant cannot be rescheduled, an effort will be made to send a tester to the individual's place of residence within the same period; (3) missing data will be examined to assess randomness. Missing data (i.e. loss to follow-up) will be tested to determine if it is informative, and the methods developed by Diggle⁸⁷ and Ridout⁸⁸ to test for completely random dropouts will be used to impute missing values. However, the primary data analysis method allows inclusion of subjects with missing data or those who terminated the study early, without relying on data imputation procedures. Furthermore, we will test whether the drop-outs are random or systematic by comparing the drop-outs with the study completers on the baseline data. The importance of missing data will be examined in the second stage of data analysis (see below).

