At the final stage, hypotheses will be tested using Mixed Effects models, a generalized linear model described by Gibbons et al.⁹¹, Hedeker et al.⁹² and Laird et al.⁹³. Responses at baseline, throughout treatment (sessions 7, 13, 21), post treatment (session 26), 3- and 6-month follow-up will be nested within subjects. Intercept and slope will be modeled as random effects nested within subject; Treatment group, time, and group-by-time interaction will be a fixed effect. A fully saturated treatment by time model will be utilized for inference. Co-variance structure will be chosen based on Akaike's Information Criterion (AIC). Data will be analyzed from all randomized subjects on whom we have a baseline assessment and at least one post-baseline evaluation. If it is needed based on analyses on stage one, baseline covariates (e.g., demographics) will also be added to the model. All hypothesis tests will be intent-to-treat, and will be two-sided at the .05 level. We will adjust p-values for multiple testing within each hypothesis separately by using a Bonferroni correction whenever more than one variable is being tested. Although we didn't have any drop-out in out pilot study, we included a drop-out rate of 10% after the baseline assessment but prior to the first post-baseline evaluation in our power analyses.

Hypothesis 1.1-1.3: Relative to those assigned to ET alone, CREST participants will show significant reduction in **hoarding severity** (primary outcome), improvement in **functioning** (both functional capacity and self-reported functioning; secondary outcomes) and improvement in **quality of life** over time.

- Independent Variables: Treatment Groups (CREST and ET), Time points (baseline, throughout treatment (sessions 7, 13, 21), post-treatment (session 26), 3 and 6-month follow-up).
- Dependent Variable: Hoarding severity (SI-R), Functioning (UPSA, USORT, SLOF, WHODAS 2.0.), Quality of Life (Neuro-QOL).

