Power analyses are performed for all hypotheses, incorporating the longitudinal nature of the design. Within this design, repeated observations within subjects are potentially correlated. This has a profound impact on the resulting tests of significance⁹⁸. When the within subject correlation is properly incorporated, the repeated measures analysis takes full advantage of all information obtained from each subject, thereby greatly increasing statistical power over methods that compare treatments cross sectionally⁹⁹. Using the method described by Diggle, Liang, & Zeger¹⁰⁰ and Ahn et al.¹⁰¹, power calculations can be made for repeated measures designs under specified assumptions. Hedeker, Gibbons, & Waternaux¹⁰² extend Diggle et al.¹⁻³'s method for various covariance structures. Procedures describes by Hedeker et al.¹⁰² for Random Regression Models which incorporated these principles was used for the proposed study to estimated needed sample size (RMASS program provided by Hedeker for the Random Regression Model). The design assumptions consist of a 2 treatment groups and up to 7 visits (baseline, sessions 7, 13, 21, 26, and 3- and 6-month follow-up) where the slope is the dependent measure. Other assumptions used were alpha-level, nature of the hypothesis (two-sided versus one-sided), drop-out rate, and variance-covariance matrix of the longitudinal data. We assume a Type-I error level (alpha-level) of .01 to 0.05, drop-out rate of 15% and an autoregressive covariance structure. Data reported in the preliminary studies section which included our own pilot studies were used to calculate effect sizes. From the preliminary analysis of pilot study, the estimated standard deviation (SD) for SI-R score ranges from 12.75-12.82 and the between visit correlation coefficient of 0.71. We considered a range of estimates of stand deviations of 12.5, 12.8 and 13.0, and correlations of .45 to 0.70 in our power analysis. We have reported large effect sizes of 1.02 and 1.51 from our previous studies which converted to differences of 60 to 37 for our primary outcome. However, for these calculations, we conservatively selected smallest clinically meaningful differences that we would like to be able to detect. This was then converted to a medium effect size, defined mathematically as a between-group difference increasing linearly from 0 at baseline to .5 SD units at the last time point. Calculations using the above assumptions indicated that the study will have minimum power of 80% to yield a statistically significant result for a medium effect size with the proposed sample size of 136 patients (68 for each of the two groups).

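### The analysis set is labelled intent-to-treat but drops randomised patients with no post-baseline visit, an exclusion the mixed model does not need (about 14 of 136 at the plan's 10% allowance)

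*Combined protocol and SAP*

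**What the plan says.** The final-stage paragraph of the Statistical Plan sets the analysis population: "Data will be analyzed from all randomized subjects on whom we have a baseline assessment and at least one post-baseline evaluation". It then states: "All hypothesis tests will be intent-to-treat, and will be two-sided at the .05 level". It lists baseline among the responses nested within subjects, with random intercept and slope and fixed effects of group, time and their interaction.

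The paragraph closes by saying that the pilot had no drop-out but that "we included a drop-out rate of 10% after the baseline assessment but prior to the first post-baseline evaluation in our power analyses". The Power Analysis section gives a different rate and no timing: "We assume a Type-I error level (alpha-level) of .01 to 0.05, drop-out rate of 15% and an autoregressive covariance structure". Both refer to a trial of 136 patients, 68 per arm.

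On missing data, the opening paragraph of the Statistical Plan says that "the primary data analysis method allows inclusion of subjects with missing data or those who terminated the study early", and that this needs no imputation. The plan also compares drop-outs with completers on baseline data and fits pattern-mixture models as sensitivity analyses. Neither passage says whether patients with only a baseline enter those models.

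**The concern.** Eligibility is decided from the baseline assessment (Recruitment and Randomization), so every randomised patient should have one. The post-baseline condition is then the only part of the rule that removes anybody, and it acts after allocation.

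The first scheduled post-baseline assessment is at session 7. Up to then CREST delivers only cognitive training while ET delivers exposure, so the arms differ in content during this window and unequal early loss is possible. If the patients who leave have unusual baselines, and more so in one arm, the remaining arms no longer have comparable baselines. Part of the difference in change is then regression to the mean rather than treatment. A likelihood model that keeps every observed baseline corrects for this under missing-at-random. The present rule gives that protection up for the earliest leavers.

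**Working it through.** **1. How many patients.** Inputs: N = 136 and the two drop-out rates.
- 10%, the rate tied to this window: 136 × 0.10 = 13.6, about 14 excluded and about 122 analysed.
- 15%, timing not stated: 136 × 0.15 = 20.4, about 20, but only if all of it fell before the first post-baseline visit. Spread evenly over the six post-baseline intervals it is 20.4 / 6 = 3.4, about 3.
- The Timeline section gives 7 waves of 9–10 patients, which is 63–70 rather than 136. At 10% that is 6–7 excluded.

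**2. The plan's power figure.** The stated minimum is 80% for a difference rising linearly from 0 to 0.5 SD. I used a generalised least squares slope test with 7 equally spaced visits, AR(1), 68 per arm and two-sided 0.05: power = Φ[(0.5/6)/SE − 1.96]. With no loss, correlations of .45 to .70 give 0.57–0.60, so 80% is not reproduced. A plain comparison of 0.5 SD at the last visit gives 0.830 with no loss, 0.790 with 10% and 0.767 with 15%. The settings of the sample-size program are not fully given, so this is a failure to reproduce and not proof of error. Only the difference between the two columns below is used here.

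| Correlation | Early loss | Baseline-only patients excluded | Kept |
|---|---|---|---|
| .45 | 10% | 53.2% | 55.2% |
| .45 | 15% | 50.9% | 53.9% |
| .70 | 10% | 55.2% | 57.1% |
| .70 | 15% | 52.9% | 55.7% |

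For example, at .45 with 10% loss the SE falls from 0.0408 to 0.0399. The gain is about 2 to 3 points throughout. Under compound symmetry it is below 1 point (90.8% to 91.3% at .45 with 10% loss).

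**3. Bias with no true effect.** The documents give no drop-out mechanism, so these scenarios are assumptions. Let baseline be standardised and let the probability of early loss follow a probit in baseline with slope b per SD and marginal rate p. The mean baseline of those who stay is

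m(p) = −[b/√(1+b²)] × φ(z_p)/(1−p).

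With baseline-to-end correlation r, the false difference in change in favour of CREST is (1−r) × [m(p_CREST) − m(p_ET)] SD. I take r from .13 to .70. The lower value is the pilot between-visit correlation of 0.71 carried over six AR(1) steps (0.71⁶ = 0.13); the upper is the top of the planned range if it applied to any pair of visits. SD = 12.8.

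Worked case, b = 1, 15% loss in ET and 5% in CREST: m(ET) = −0.194, m(CREST) = −0.077, gap 0.117. At r = .13: 0.87 × 0.117 = 0.102 SD, or 1.3 points. At r = .70: 0.30 × 0.117 = 0.035 SD, or 0.45 points.

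| Loss ET v CREST | b | Gap in m (SD) | Bias, r = .70 to .13 (points) |
|---|---|---|---|
| 12.5% v 7.5% | 0.25 | 0.020 | 0.08 to 0.22 |
| 15% v 5% | 0.25 | 0.040 | 0.15 to 0.45 |
| 12.5% v 7.5% | 1 | 0.058 | 0.22 to 0.65 |
| 15% v 5% | 1 | 0.117 | 0.45 to 1.3 |

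A slope of 1 is strong: with 15% loss, ET leavers start about 1.3 SD (17 points) worse than ET stayers. A slope of 0.25 puts them about 0.44 SD (6 points) worse.

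A separate simulation of 8,000 runs per scenario, with about 9–10% early loss, found no bias when loss was random or depended on baseline equally in both arms. It found 0.05–0.09 SD (0.6–1.2 points) when the dependence ran in opposite directions by arm. Keeping the baseline-only patients brought the bias to about zero.

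For scale, the planned effect is 0.5 × 12.8 = 6.4 points, so the range runs from about 1% (0.08/6.4) to 20% (1.3/6.4) of it.

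**The case against.** The best defence is that few patients may be affected. The 10% is an allowance made despite a pilot with no drop-out, and the Retention section reports 0% attrition in two open trials. Exclusion requires missing all six post-baseline assessments; stopping treatment early does not trigger it, and one later visit brings a patient back in. Assessments take place in the home, and the plan describes steps to recover missing data. The upper bias figures need steep, unequal drop-out that no figure in the documents supports. The drop-out comparison and the pattern-mixture models offer some protection.

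Most of this stands, and it limits the size of the problem. It does not defend the rule. The comparison with completers can reveal severity-related loss but does not correct the primary estimate, and the pattern-mixture models are not said to restore these patients.

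Two stronger readings should be resisted. A reader might infer that 14 to 20 patients will be lost. The documents give planning rates only, and 20 requires placing all of an untimed 15% in this window. A reader might also take the 3 CREST and 5 control losses in the group's current trial as a sign of differential early loss. Those counts have no denominator and no timing, so they show neither.

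**Conclusion.** The inconsistency is plain from the text: a set conditioned on a post-randomisation event is described as intent-to-treat, in a model that can use the excluded patients. About 14 of 136 would be excluded at the 10% allowance, and fewer if retention matches the pilot.

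The consequence is modest and conditional. Bias arises only if early loss depends on baseline severity and does so differently by arm, through either its rate or its direction. It is then about 0.1 to 0.5 points for weak dependence and 0.2 to 1.3 for strong dependence, under the assumed loss rates, SD 12.8 and correlations of .13 to .70. The documents do not support saying that the trial's result will be biased. That retention removes the bias rests on missing-at-random and an adequate covariance model. The change is still worth making, because it costs almost nothing and makes the primary analysis match its label.

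**What to change.** Replace the analysis-set sentence with: *All randomised patients with a baseline SI-R are analysed in the arm assigned; baseline is a response in the model, so patients without a post-baseline visit are kept.* Apply the same rule to each other outcome, using that outcome's own baseline. Then:
- keep the present set as a sensitivity analysis only;
- state that baseline-only patients are included in the pattern-mixture analysis;
- report losses before the first post-baseline evaluation by arm;
- reconcile the 10% and 15% drop-out rates and say when each applies.

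The cost is one replaced sentence and a few lines of clarification in the Statistical Plan and Power Analysis sections. No new data, visits or patients are needed.

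### Single-step Bonferroni on the four functioning outcomes is valid but conservative; Holm keeps the same familywise error and can only add power, by roughly 0 to 11 points per outcome

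*Combined protocol and SAP*

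**What the plan says.** The final-stage paragraph of the Statistical Plan sets the level, "All hypothesis tests will be intent-to-treat, and will be two-sided at the .05 level", and then the multiplicity rule: "adjust p-values for multiple testing within each hypothesis separately by using a Bonferroni correction whenever more than one variable is being tested". The Statistical Analysis entry under Hypothesis 1.1-1.3 repeats the rule. No stepwise procedure is mentioned anywhere.

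Hypotheses 1.1-1.3 cover three domains. Hoarding severity is measured by SI-R alone and quality of life by Neuro-QoL alone. The functioning domain, described as "both functional capacity and self-reported functioning; secondary outcomes", has four measures, listed as "Functioning (UPSA, USORT, SLOF, WHODAS 2.0". Read as three hypotheses, the rule affects only the functioning family among the treatment comparisons.

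The Power Analysis section states a minimum power of 80% for a medium effect with 68 patients per group. Its standard deviations are SI-R figures. It gives no standard deviation or effect size for any functioning measure, and no correlation between outcomes.

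**The concern.** Single-step Bonferroni compares all four p-values with .0125, whatever the other three show. Holm starts at the same threshold and relaxes it as outcomes are rejected: the smallest p-value is compared with .05/4 = .0125, the next with .05/3 = .0167, then .05/2 = .025, then .05, stopping at the first failure. It controls the familywise error strongly at .05 under any dependence, so it needs no assumption that Bonferroni does not also need, and its rejections always include Bonferroni's.

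At stake is power on the secondary claims. The trial predicts benefit on both functional capacity and self-reported functioning. If that is right, several of the four outcomes carry real effects, and this is the situation in which the single-step rule loses most.

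**Working it through.** **1. The plan's own 80%.** Inputs from the Power Analysis section: 68 per group, 7 visits, slope as the dependent measure, autoregressive covariance, a "between-group difference increasing linearly from 0 at baseline to .5 SD units at the last time point", and "correlations of .45 to 0.70 in our power analysis". For alpha and drop-out: "We assume a Type-I error level (alpha-level) of .01 to 0.05, drop-out rate of 15% and an autoregressive covariance structure". My assumptions: equally spaced visits, a common baseline mean, and all drop-out straight after baseline.

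With t = 0, 1/6, ..., 1 and correlation ρ, the information per patient is I = (1 − drop-out) × Σ(t_j − ρ·t_(j−1))² / (1 − ρ²), and power = Φ(0.5·√(68·I/2) − z).

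At ρ = .70:
- The sum is (1.0² + 1.3² + 1.6² + 1.9² + 2.2² + 2.5²)/36 = 19.95/36 = 0.554.
- Dividing by 0.51 gives 1.087, and multiplying by 0.85 gives I = 0.924.
- 0.5·√(34 × 0.924) = 2.80.
- Power at .05 is Φ(2.80 − 1.96) = 80.0%.

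The same formula gives 82.6% at ρ = .60 and 88.1% at .45, so the stated minimum reproduces at alpha .05. At alpha .01 it gives 59-71%, so the minimum does not reproduce at the lower end of the stated alpha range. The Statistical Plan gives a different drop-out figure ("we included a drop-out rate of 10% after the baseline assessment but prior to the first post-baseline evaluation in our power analyses"). Using 10% gives 82.2% at ρ = .70, which does not alter the point.

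**2. Bonferroni on four outcomes.** Assume each functioning outcome has the 80% that the plan derives from SI-R inputs. The mean of the test statistic is 1.96 + 0.84 = 2.80. The two-sided critical value at .0125 is 2.50. Power per outcome is Φ(2.80 − 2.50) = 62%.

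**3. Holm on the same outcomes.** Simulation with 400,000 draws per scenario: four equicorrelated normal test statistics, mean 2.80 where the effect is real and 0 where it is not. The correlation and the number of real effects are assumptions, so both are varied.

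| Real effects (of 4) | Bonferroni, average power | Gain with Holm, correlation 0 to .5 | Gain at correlation .9 |
|---|---|---|---|
| 4 | 62% | 10.8 to 9.0 points (72.8% to 71.0%) | 6.8 points |
| 3 | 62% | 5.8 to 5.0 points | 4.1 points |
| 2 | 62% | 2.5 to 2.2 points | 1.9 points |
| 1 | 62% | about 0.1 points | about 0 |

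With four real effects, the chance that all four are significant rises from 15% to 38% at correlation 0, and from 31% to 53% at .5. The chance of at least one significant outcome does not change (97.9% at correlation 0, 88.5% at .5), because the first Holm step is the Bonferroni test.

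**4. Other starting points, four real effects.** If unadjusted power is only 53-60% per outcome, the gain is 5-7 points. If 80% already held at .0125, Holm would raise it to 87-89%.

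**5. Familywise error.** It stays at or below 5% for both methods in every scenario. With three of four effects real, the chance of falsely rejecting the fourth is about 3% with Holm and about 1% with Bonferroni.

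**6. Family of six.** If Hypotheses 1.1-1.3 were instead one family, each test would be at .05/6 = .0083. Bonferroni power would be about 57%, and Holm would add 9.5 to 11.8 points with all six effects real (correlation .7 to 0).

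**The case against.** The pre-specified rule is valid. It controls the familywise error, biases nothing and contradicts nothing else in the plan. That stands: this is a choice between two valid procedures.

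A reader might infer from the best case that Holm recovers 9-11 points on every functioning outcome at no cost. The documents do not support that. It needs a true effect on all four measures, about 80% unadjusted power on each, and a correlation between outcomes of about .5 or less. None of these is documented for functioning, and two performance tests plus two questionnaires need not respond alike. In favour of the larger figure, benefit in both functioning domains is the trial's own hypothesis, so several real effects is a fair planning case. It is not an established one.

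The costs are small but real:
- Holm has no simple matching simultaneous intervals. If intervals are reported at the Bonferroni level, an outcome can be Holm-significant while its interval includes zero. The plan asks for no simultaneous intervals on these outcomes.
- Under partial nulls Holm uses more of the 5%, while staying within it. Bonferroni also bounds the expected number of false rejections at .05. Holm does not: with one or two very strong effects and the rest null, simulated values were .051-.065. The plan sets no target for that quantity.
- The general rule precedes all the hypotheses and so may reach the mediation analyses (2.1 and 2.2), which rest on bootstrap 95% intervals. Bonferroni carries over directly to interval levels; Holm adjusted p-values do not. The change should therefore not extend to them.

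The sponsor could also note that the stated alpha range of .01 to .05 includes .0125. The 80% does not reproduce at .01, and from 80.0% at .05 it falls to 62% at .0125. Even if it did hold there, Holm would still add power.

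**Conclusion.** The point holds as an optional efficiency gain. Testing each functioning outcome at .0125 is correct but more conservative than the plan's own error target requires, and for the tests themselves Holm never does worse. From 62% average power the gain is up to 9-11 points with four real effects (about 7 if the outcomes are very highly correlated), 4-6 with three, 2-3 with two and about 0 with one. These figures assume 80% unadjusted power and an equal effect on each affected outcome, neither of which the documents give for functioning.

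A reader might also infer that the primary analysis loses power. Under the three-hypothesis reading it does not: SI-R and Neuro-QoL are each tested alone at .05 and gain nothing. Only if 1.1-1.3 were one family of six would SI-R be affected, and the wording that the correction is applied within each hypothesis separately points away from that.

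**What to change.** In the final-stage paragraph of the Statistical Plan and in the Statistical Analysis entry under Hypothesis 1.1-1.3, specify Holm step-down adjusted p-values in place of the Bonferroni correction for any treatment-comparison family with more than one outcome. Limit the change to Hypotheses 1.1-1.3. If the mediation analyses (2.1 and 2.2) are adjusted, keep their bootstrap intervals at the Bonferroni level. If simultaneous intervals are reported for functioning, keep those at the Bonferroni level too, and state that they may not match the Holm decision.

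Date the amendment before anyone sees outcome data by arm, since a later switch would look data-driven. The cost is a short text edit and a line of code, with no added patients, visits or alpha. What is given up is the exact match between tests and simple simultaneous intervals, and some of Bonferroni's slack below 5%.

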- Statistical Analysis: The dependent variable will be analyzed by mixed effects model methods as described above. Baseline demographic and other clinically important characteristics at baseline will be assessed for imbalance between the two groups and their association with the outcome using a univariate analysis. Those found to be significantly unbalanced between intervention groups (p < 0.10) and moderately associated with the outcome (p < 0.15) will be included as covariates in the model. We will adjust p-values for multiple testing within each hypothesis separately by using a Bonferroni correction whenever more than one variable is being tested

Hypotheses 2.1: Treatment adherence, improvement in executive functioning, and reduction in avoidance will mediate hoarding symptom reduction in CREST.

Dependent Variables: Hoarding severity (SI-R)

Independent Variables: Executive Functioning (D-KEFS scaled scores and PCET), Avoidance (AAQ and BAT) and Treatment Adherence score.

Statistical Analysis: The effect of mediator variables will be tested following the procedures recommended by Kraemer⁹⁴, Bauman⁹⁵, Cohen and Cohen⁹⁶, and Busemeyer and Jones⁹⁷. Briefly, treatment mediators explain how or why one variable affects the treatment effect and are defined as mechanisms through which a treatment might achieve its effects. The mediator's effect is measured during the treatment and is correlated with treatment choice and may possibly be a result of treatment and have either a main or interactive effect on the outcome. The dependent or outcome measure (SI-R) will be evaluated throughout the study and will be used as a repeated measure for all the available time points. In essence, the slope of each outcome measure on time will be used as a dependent measure. The mediator and bootstrap technique will be used to calculate a 95% confidence interval for mediation effect. Random effects models will be used for analysis and the change score of mediators will be included in the model.

Hypotheses 2.2: Symptom severity reduction and improved functional capacity will mediate improved quality of life in CREST.

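### The 80% power stated for all hypotheses over alpha .01 to .05 is reproduced only at .05, not at .01 or at the .0125 that the four functioning measures would get

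*Combined protocol and SAP*

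**What the plan says.** **Level and adjustment.** The Statistical Plan states: "All hypothesis tests will be intent-to-treat, and will be two-sided at the .05 level". It then applies a Bonferroni correction "within each hypothesis separately by using a Bonferroni correction whenever more than one variable is being tested", and the same sentence is repeated in the analysis paragraph for Hypothesis 1.1-1.3.

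**The hypotheses.** Three hypotheses share one heading, which begins "Hypothesis 1.1-1.3: Relative to those assigned to ET alone, CREST participants will show significant reduction in". Hoarding severity is labelled primary and functioning secondary; the Measures section also labels quality of life secondary. One dependent-variable line serves all three: "Hoarding severity (SI-R), Functioning (UPSA, USORT, SLOF, WHODAS 2.0.), Quality of Life (Neuro-QOL". That is six measures in three groups. Hypotheses 1.1, 1.2 and 1.3 are not written out one by one.

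**Power.** The Power Analysis says that calculations were made for all hypotheses. It states: "We assume a Type-I error level (alpha-level) of .01 to 0.05, drop-out rate of 15% and an autoregressive covariance structure". It gives correlations of .45 to .70, up to 7 visits with the slope as the dependent measure, and a between-group difference growing linearly from 0 at baseline to .5 SD at the last visit. It concludes that power is at least 80% with 136 patients, 68 per group. It does not say which alpha goes with which hypothesis, or how the range relates to the Bonferroni rule.

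**The concern.** A minimum of 80% over a range of alphas has to hold at the smallest of them, and the required critical value rises from 1.960 at .05 to 2.576 at .01. A design that just reaches 80% at .05 cannot also reach it at .01 for the same effect and sample size. The lower alphas matter because the plan's own rule produces one: four functioning measures under a single hypothesis are each tested at .05/4 = .0125. If 80% holds only at .05, the plan overstates its chance of detecting a medium effect on functioning. A null result there could then be read as stronger evidence of no benefit than it is.

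A smaller issue is that the alpha for SI-R has to be inferred. If the shared block were treated as one family, a primary p-value between .0083 and .05 would change from success to failure, and nothing in the text settles this before the data are seen.

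**Working it through.** **Inputs from the Power Analysis.** 68 per group; 15% drop-out; 7 visits; AR(1) with r from .45 to .70; difference 0 to 0.5 SD, linear; alpha .01 to .05; two-sided tests (Statistical Plan).

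**My assumptions, because program settings are not given.** Visits equally spaced (t = 0 to 6); drop-out taken as a cut in n from the start, so n = 68 × 0.85 = 57.8 per group; normal approximation; outcomes in SD units. The plan gives an SD and a correlation for SI-R only, so the same inputs are carried over to the functioning measures.

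**Formula.** Slope difference per visit: δ = 0.5/6 = 0.0833. Standard error: SE = √(2v/n), where v is the variance of one subject's generalised least squares slope and V has entries r^|j−k|. With equal baseline means, v = 1/(t′V⁻¹t). With free intercepts, v is the slope element of (X′V⁻¹X)⁻¹, with X = [1, t]. Power = Φ(δ/SE − z), with z = 1.960, 2.498, 2.576 and 2.638 at alpha .05, .0125, .01 and .0083.

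**Step 1: reproduce the 80%.** Equal baseline means, r = .70: v = 0.02556, SE = √(2 × 0.02556/57.8) = 0.02974, δ/SE = 2.802. Power at .05 = Φ(2.802 − 1.960) = Φ(0.842) = 80.0%. This matches the plan's figure at the least favourable end of its correlation range.

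**Step 2: lower the alpha.**

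| Model | r | v | δ/SE | .05 | .0125 | .01 |
|---|---|---|---|---|---|---|
| Equal baselines | .45 | 0.02038 | 3.138 | 88.1% | 73.9% | 71.3% |
| Equal baselines | .70 | 0.02556 | 2.802 | 80.0% | 62.0% | 58.9% |
| Free intercepts | .45 | 0.05104 | 1.983 | 50.9% | 30.3% | 27.7% |
| Free intercepts | .70 | 0.04857 | 2.033 | 52.9% | 32.1% | 29.4% |

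With free intercepts, power dips by up to a point at intermediate r (50.2%, 29.7% and 27.1% at r = .55).

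**Step 3: sensitivity, equal baselines.**
- The Statistical Plan gives a different loss rate ("we included a drop-out rate of 10% after the baseline assessment"). At 10%, n = 61.2, and the best case (r = .45) is 76.8% at .0125 and 74.3% at .01.
- With no drop-out, r = .45 gives 81.8% at .0125 and 79.6% at .01.
- With time in weeks instead of equal steps (0, 7, 13, 21, 26, 39, 52, taking sessions as weekly; correlation still by visit) and 15% drop-out, power is 78-84% at .05, 59-67% at .0125 and 56-64% at .01.

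**Step 4: the six-variable family.** .05/6 = .0083. A design with exactly 80% at .05 has Φ(1.960 + 0.842 − 2.638), about 56%, at .0083, whatever the model.

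**The case against.** **The plan does not clearly put SI-R at .0083.** A reader might infer that it does, since six measures sit under one heading with the Bonferroni sentence repeated inside. The text points the other way. Adjustment is within each hypothesis separately, the heading numbers three hypotheses, the outcomes come in three groups in the same order, and SI-R is labelled primary. The natural mapping is SI-R alone at .05, four functioning measures at .0125 each and Neuro-QoL at .05. This stands. What remains is that the mapping is not written down.

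**The free-intercept figures are not the cost of multiplicity.** A reader might infer from 28-32% that the adjustment alone ruins the study. That model gives only about 51-53% even at .05, so most of its distance from 80% has nothing to do with alpha. It cannot be dismissed, because the analysis model includes a group effect as well as group-by-time, but it is one end of a range.

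**80% at .01 is not impossible in general.** Under compound symmetry at r = .70, with 15% drop-out and equal spacing, power at .01 is 96.0% with free intercepts and 97.9% with equal baselines. This is true, but the plan states an autoregressive structure, and no AR(1) variant I ran with 15% drop-out reached 80% at .0125 or .01.

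**The range may only list values explored, with 80% meant for .05.** This is plausible. The adjusted tests would then have no stated power at all, and the same correction is needed.

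**Conclusion.** The power statement is not supported as written. On the stated AR structure, correlations and 15% drop-out, the 80% is reproduced at alpha .05 with equal baseline means (80-88%). It is not reached at .0125 (62-74%) or .01 (59-71%), and the free-intercept version is lower throughout. For the four functioning measures the shortfall against 80% is thus 6 to 18 points in the model most favourable to the plan. These figures rest on my assumptions about spacing, baseline means and drop-out. The sensitivity checks move them by several points, but at the stated drop-out none restores 80% at the lower alphas.

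The undefined family is minor. It does not show that the primary test is underpowered: read as probably intended, SI-R is tested at .05, the one level at which the stated power can be reproduced.

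**What to change.** 1. In the Power Analysis, replace the statement "We assume a Type-I error level (alpha-level) of .01 to 0.05" with the alpha each hypothesis will use: two-sided .05 for SI-R, .0125 for each of the four functioning measures and .05 for Neuro-QoL. Give the power at each, showing the lower value for functioning.
2. State the settings behind the figures: model (free intercepts or equal baseline means), visit spacing, covariance, correlation and a single drop-out rate, reconciling 10% with 15%.
3. Add one sentence under Hypothesis 1.1-1.3: 1.1 is SI-R alone; 1.2 is UPSA, U-SORT, SLOF and WHODAS 2.0, Bonferroni-adjusted over four; 1.3 is Neuro-QoL.

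The cost is a few sentences and one rerun of the power program. Sample size and data collection do not change. The downside is a less favourable stated power for functioning.
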